The atezolizumab dose may be interrupted for up to 12 weeks for Grade ≥ 3 toxicity or adverse event. If the adverse event does not resolve to Grade ≤ 1 within 12 weeks of last dose of atezolizumab, further treatment with atezolizumab will be discontinued.

There will be no dose reduction for atezolizumab in this study. Patients may temporarily suspend study treatment for up to 12 weeks beyond the last dose if they experience adverse events that require a dose to be withheld. If atezolizumab is withheld because of adverse events for > 12 weeks beyond the last dose, then the patient will be discontinued from atezolizumab treatment and will be followed up for safety and efficacy as specified in Section 4.5.11.

If, in the judgment of the investigator, the patient is likely to derive clinical benefit from atezolizumab after a hold of > 12 weeks, study drug may be restarted with the approval of the Medical Monitor.

If a patient must be tapered off steroids used to treat adverse events, atezolizumab may be held for additional time beyond 12 weeks from the last dose until steroids are discontinued or reduced to prednisone dose ≤ 10 mg/day (or dose equivalent). The acceptable length of interruption will depend on an agreement between the investigator and the Medical Monitor.

Guidelines for treatment interruption or discontinuation and for the management of specific adverse events are provided in Section 5.1.3.

Any overdose or incorrect administration of study drug should be noted on the Study Drug Administration electronic Case Report Form (eCRF). Adverse events associated with an overdose or incorrect administration of study drug should be recorded on the Adverse Event eCRF.

Refer to the pharmacy manual for detailed instructions on drug preparation, storage, and administration.

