4.5.9 Assessments during Treatment

All visits must occur within ± 3 days from the scheduled date unless otherwise noted (see [Appendix 1](#) and [Appendix 2](#)). All assessments involving cystoscopy and urine cytology will be performed within 21 days prior to atezolizumab treatment and for patients in Cohorts 1b, 2, and 3, 14–21 days prior to BCG dosing unless otherwise specified.

See the study flowchart provided in [Appendix 1](#) and [Appendix 2](#) for the schedule of treatment period assessments.

If scheduled dosing and study assessments are precluded because of a holiday, weekend, or other event, then dosing may be postponed to the soonest following date, with subsequent dosing continuing on the original 12-week schedule (for atezolizumab and BCG Induction course/Maintenance Course 1), 24-week schedule (for atezolizumab and BCG Maintenance Courses 2–5), or 21-day cycle schedule (for single-agent atezolizumab). If treatment was postponed for fewer than 3 days, the patient can resume the original schedule. Resumption of therapy beyond 3 days will require approval by the Medical Monitor.

Following the eighth cycle of atezolizumab, one of three subsequent administrations may be delayed by 28 days in the combination cohorts to allow for vacations. Following the eighth cycle of atezolizumab, one of three subsequent administrations may be delayed by 1 week for atezolizumab alone cohort to allow for vacations.

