5.1.3 Management of Patients Who Experience Specific Adverse Events

There will be no dose reduction for atezolizumab in this study. Patients may temporarily suspend atezolizumab for up to 12 weeks beyond last dose if they experience adverse events that require a dose to be withheld. If atezolizumab is withheld because of related adverse events for > 12 weeks beyond the last dose, then the patient will be discontinued from atezolizumab and will be followed for safety and efficacy as specified in Section 5.5. If, in the judgment of the investigator, the patient is likely to derive clinical benefit from resuming atezolizumab after a hold > 12 weeks, atezolizumab may be restarted with the approval of the Medical Monitor.

If a patient must be tapered off steroids used to treat adverse events, atezolizumab may be withheld for an additional time beyond 12 weeks from the last dose until steroids are discontinued or reduced to prednisone dose (or dose equivalent) ≤ 10 mg/day. The acceptable length of interruption will depend on agreement between the investigator and the Medical Monitor.

Note, if systemic corticosteroids must be initiated in patients receiving weekly BCG installations, either during BCG induction or any BCG maintenance course, BCG must be withheld throughout the duration of systemic corticosteroid therapy to minimize the risk of systemic BCG infection. BCG instillations should not be resumed until the patient has discontinued systemic corticosteroids.

Dose interruptions for reason(s) other than toxicity, such as surgical procedures, may be allowed with Medical Monitor approval. The acceptable length of interruption will depend on agreement between the investigator and the Medical Monitor.

Guidelines for the management of fever, local bladder symptoms, and influenza-like illness are presented in [Table 8](#), as these events may result from or be potentiated by the combination of BCG and atezolizumab. Refer to [Appendix 12](#) for additional management guidelines for immune-mediated adverse events.

See Section 4.3.2.1 for guidelines for the management of infusion-related reactions and [Appendix 8](#) for precautions for anaphylaxis.

Table 8 Guidelines for Management of Specific Adverse Events

Severity	Management
Influenza-like illness	
Arthralgia/chills	
Grade ≤ 2	
 Continue atezolizumab. Treat symptoms with non-steroidal anti-inflammatory drugs (e.g., ibuprofen).

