Atezolizumab treatment may be temporarily suspended in patients experiencing toxicity considered to be related to study treatment. If corticosteroids are initiated for treatment of the toxicity, they must be tapered over ≥ 1 month to ≤ 10 mg/day oral prednisone or equivalent before atezolizumab can be resumed. If atezolizumab is withheld for > 12 weeks after event onset, the patient will be discontinued from atezolizumab. However, atezolizumab may be withheld for > 12 weeks to allow for patients to taper off corticosteroids prior to resuming treatment. Atezolizumab can be resumed after being withheld for > 12 weeks if the Medical Monitor agrees that the patient is likely to derive clinical benefit. Atezolizumab treatment may be suspended for reasons other than toxicity (e.g., surgical procedures) with Medical Monitor approval. The investigator and the Medical Monitor will determine the acceptable length of treatment interruption.

Appendix 12

Risks Associated with Atezolizumab and Guidelines for Management of Adverse Events Associated with Atezolizumab (cont.)

MANAGEMENT GUIDELINES

PULMONARY EVENTS

Dyspnea, cough, fatigue, hypoxia, pneumonitis, and pulmonary infiltrates have been associated with the administration of atezolizumab. Patients will be assessed for pulmonary signs and symptoms throughout the study and will also have computed tomography (CT) scans of the chest performed at every tumor assessment.

All pulmonary events should be thoroughly evaluated for other commonly reported etiologies such as pneumonia or other infection, lymphangitic carcinomatosis, pulmonary embolism, heart failure, chronic obstructive pulmonary disease, or pulmonary hypertension. Management guidelines for pulmonary events are provided in [Table 1](#).

Appendix 12

Risks Associated with Atezolizumab and Guidelines for Management of Adverse Events Associated with Atezolizumab (cont.)

Table 1 Management Guidelines for Pulmonary Events, Including Pneumonitis

Event	Management
Pulmonary event, Grade 1	
 • Continue atezolizumab and monitor closely. • Re-evaluate on serial imaging. • Consider patient referral to pulmonary specialist.

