Pulmonary event, Grade 2	
 • Withhold atezolizumab for up to 12 weeks after event onset.^a • Refer patient to pulmonary and infectious disease specialists and consider bronchoscopy or BAL. • Initiate treatment with 1–2 mg/kg/day oral prednisone or equivalent. • If event resolves to Grade 1 or better, resume atezolizumab.^b • If event does not resolve to Grade 1 or better while withholding atezolizumab, permanently discontinue atezolizumab and contact Medical Monitor.^c • For recurrent events, treat as a Grade 3 or 4 event.
Pulmonary event, Grade 3 or 4	
 • Permanently discontinue atezolizumab and contact Medical Monitor.^c • Bronchoscopy or BAL is recommended. • Initiate treatment with 1–2 mg/kg/day oral prednisone or equivalent. • If event does not improve within 48 hours after initiating corticosteroids, consider adding an immunosuppressive agent. • If event resolves to Grade 1 or better, taper corticosteroids over ≥ 1 month.

BAL = bronchoscopic alveolar lavage.

- ^a Atezolizumab may be withheld for a longer period of time (i.e., > 12 weeks after event onset) to allow for corticosteroids (if initiated) to be reduced to ≤ 10 mg/day oral prednisone or equivalent. The acceptable length of the extended period of time must be agreed upon by the investigator and the Medical Monitor.
- ^b If corticosteroids have been initiated, they must be tapered over ≥ 1 month to ≤ 10 mg/day oral prednisone or equivalent before atezolizumab can be resumed.
- ^c Resumption of atezolizumab may be considered in patients who are deriving benefit and have fully recovered from the *immune-mediated* event. Patients can be re-challenged with atezolizumab only after approval has been documented by both the investigator (or an appropriate delegate) and the Medical Monitor.

Appendix 12

Risks Associated with Atezolizumab and Guidelines for Management of Adverse Events Associated with Atezolizumab (cont.)

HEPATIC EVENTS

Immune-mediated hepatitis has been associated with the administration of atezolizumab. Eligible patients must have adequate liver function, as manifested by measurements of total bilirubin and hepatic transaminases, and liver function will be monitored throughout study treatment. Management guidelines for hepatic events are provided in [Table 2](#).

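### The 12-week limit on holding atezolizumab runs from the last dose in Sections 4.3.2.1 and 5.1.3 but from event onset in Appendix 12, event scope differs, and the Grade 3 or higher hold rule has no exception for events that Appendix 12 stops permanently

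*Combined protocol and SAP*

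**What the plan says.** Three places set the default rule for stopping atezolizumab after a long hold.

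- Section 4.3.2.1 stops treatment "If atezolizumab is withheld because of adverse events for > 12 weeks beyond the last dose". Its preceding paragraph allows a hold of up to 12 weeks for any Grade 3 or higher event, and ends treatment if the event has not come down to Grade 1 or lower within 12 weeks of the last dose.
- Section 5.1.3 stops treatment "If atezolizumab is withheld because of related adverse events for > 12 weeks beyond the last dose".
- Appendix 12, under Treatment Interruption, allows suspension for "toxicity considered to be related to study treatment" and then stops treatment on a different clock: "If atezolizumab is withheld for > 12 weeks after event onset". Its tables repeat that origin, for example in Table 1 for Grade 2 pulmonary events: "Withhold atezolizumab for up to 12 weeks after event onset".

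All three allow a longer hold for steroid taper (in Appendix 12, "atezolizumab may be withheld for > 12 weeks to allow for patients to taper off corticosteroids"), and all three allow restart after 12 weeks with the Medical Monitor's agreement.

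For a set of serious events Appendix 12 gives no hold and requires permanent discontinuation. Examples are Grade 3–4 pulmonary, hepatic, ocular, myocarditis, neuropathy and renal events, and myasthenia gravis, Guillain-Barré syndrome and meningoencephalitis at any grade. This list is not exhaustive. For most of these, rechallenge is possible only after full recovery and with approval documented by both the investigator and the Medical Monitor.

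**The concern.** These are operative dosing rules for the same decision, and they can give different answers for the same patient. Someone may be past the mandatory stop under the body text and still inside the limit under Appendix 12, or the reverse. The difference decides who must approve the next dose. Under one text the investigator resumes on resolution; under the other the patient is already off treatment unless the Medical Monitor agrees.

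The Grade 3 or higher rule raises a separate point. A site that works from Section 4.3.2.1 could hold a patient with Grade 3 pneumonitis and resume once the event reaches Grade 1, whereas Appendix 12 would have stopped the drug and set stricter conditions for going back.

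What is at stake is patient safety, exposure, and the consistency of one planned safety summary, adverse events leading to withdrawal of treatment (Section 6.5), in cohorts of about 8 to 18 patients before expansion. Section 1.4 itself holds that toxicity tolerated in metastatic disease is not acceptable in this early setting.

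**Working it through.** **Clock.** Inputs: 12 weeks = 84 days in every text; atezolizumab every 21 days (Section 4.3.2.1); and, after the eighth cycle, Section 4.5.9 states that "one of three subsequent administrations may be delayed by 28 days in the combination cohorts" and that "one of three subsequent administrations may be delayed by 1 week for atezolizumab alone cohort". The visit window of ±3 days is ignored.

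Let the last dose be day 0 and event onset day d.

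- Body limit = 84.
- Appendix 12 limit = d + 84.
- Gap = d.

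| Onset d | Body limit | Appendix 12 limit | Gap (days) |
|---|---|---|---|
| −7 (before last dose) | 84 | 77 | −7 |
| 0 | 84 | 84 | 0 |
| 7 | 84 | 91 | 7 |
| 14 | 84 | 98 | 14 |
| 21 (next dose due) | 84 | 105 | 21 |
| 28 (Cohort 1A, 21 + 7) | 84 | 112 | 28 |
| 49 (combination, 21 + 28) | 84 | 133 | 49 |

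The last row takes the 28 days as added to the 21-day cycle. If a 28-day interval is meant, the combination cohorts also reach day 112. Both delayed rows need onset at the very end of a vacation delay.

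**Worked case.** A related Grade 2 ocular event starts on day 20, is treated topically as Appendix 12 Table 5 directs, and reaches Grade 1 on day 91. Appendix 12 limit: 20 + 84 = day 104, so the table says to resume. Body limit: day 84, so the patient has been discontinued for a week and restart needs the Medical Monitor. Treatment is topical, so the allowance for tapering systemic steroids does not naturally apply.

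**Scope.** The stop in Section 4.3.2.1 has no causality condition. The stop in Section 5.1.3 is limited to related events, and Appendix 12 frames its rule around related toxicity. That makes two scopes. A long hold for an unrelated event is a mandatory stop under Section 4.3.2.1 only.

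**Grade 3 or higher.** Side by side:

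- Section 4.3.2.1: a hold is allowed for any such event. It ends in discontinuation if the event is not down to Grade 1 within 12 weeks of the last dose, and resumption during a steroid taper waits for prednisone of 10 mg/day or less.
- Appendix 12: permanent stop for the events listed above, with rechallenge generally requiring full recovery and dual documented approval.

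Within Section 4.3.2.1 the only event-specific stop is Table 7, for Grade 3 or 4 infusion-related reactions.

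**How many patients.** The documents give related Grade 3–4 rates for metastatic monotherapy: raised ALT 3/119 (2.5%, Section 1.3.4) and 4/310 (1.3%, Section 1.3.4.1), and pneumonitis 2/310 (0.6%, Section 1.3.4.1). Assuming that these carry over to about 70 patients:

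- ALT: 70 × 4/310 = 0.90 to 70 × 3/119 = 1.76.
- Pneumonitis: 70 × 2/310 = 0.45.
- Sum: 1.35 to 2.22 expected events.

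This is an expected count for two event types only. Its upper end pairs ALT from one cohort with pneumonitis from another, and only events handled under Section 4.3.2.1 alone would be managed differently.

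**The case against.** The strongest reply is that the texts can be reconciled in practice. The Grade 3 or higher sentence is permissive. Section 4.3.2.1 sends the reader to Section 5.1.3 for interruption and discontinuation, and Section 5.1.3 sends the reader on to Appendix 12 for immune-mediated events. On an ordinary reading the event-specific rule overrides the general permission. Every text also has the same Medical Monitor route to restart after 12 weeks, so the default clock will rarely settle the outcome alone.

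Much of this stands, and it keeps the effect small. It does not remove the conflict. Section 5.1.3 restates the last-dose clock before pointing to an appendix that uses the other one, and it calls that appendix additional guidance. The shared override leaves open whether approval is needed in the disputed window.

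Stronger readings are tempting, and the documents do not support them:

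- A reader might infer that Section 4.3.2.1 sets no conditions for restart. It does: Grade 1 or lower, the prednisone threshold, and Medical Monitor approval after 12 weeks. What it lacks is full recovery and dual approval.
- A reader might count three triggers from the three wordings. The wordings in Section 5.1.3 and Appendix 12 match in substance.
- A reader might infer that a dangerous restart could pass unnoticed. Section 4.6.2 stops treatment for unacceptable immune-mediated events, and Section 5.2.3 requires most of the events concerned to be reported within 24 hours.

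**Conclusion.** The inconsistency is real and lies in the current text. The default mandatory stop differs by 0 to 21 days on schedule, assuming onset between the last dose and the next one due. The gap can reach 28 to 49 days after a permitted delay, depending on how the 28 days in Section 4.5.9 are read. Two causality scopes are in use, and no sentence makes Appendix 12 prevail over the general Grade 3 or higher hold.

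The severity is low. Few patients would be managed differently; the expected count above depends on metastatic rates carrying over, and the share of sites that would apply Section 4.3.2.1 alone is unknown. No sample size, confidence interval or efficacy analysis changes, since Section 6 includes every treated patient. The case for acting is that stop rules for serious immune-mediated toxicity should read the same wherever a site looks, and that the withdrawal count should mean the same thing at every site.

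**What to change.** Three wording changes in the next amendment:

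1. In Section 4.3.2.1, qualify the Grade 3 or higher hold: *except where Appendix 12 requires permanent discontinuation, in which case Appendix 12 governs, including its conditions for rechallenge.*
2. Use one clock throughout. The smaller edit is to change Sections 4.3.2.1 and 5.1.3 to event onset, matching Appendix 12. The drawback is that the default stop then usually falls up to 3 weeks later than now. If the sponsor prefers the tighter last-dose clock, about 15 cells in the Appendix 12 tables, their footnotes and the Treatment Interruption paragraph must change.
3. Use one event scope. Limiting the stop in Section 4.3.2.1 to related adverse events would match the other two places. Long holds for unrelated events would then lose their automatic stop, and the sponsor should confirm that this is intended.

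The cost is drafting only, with no change to design, sample size or analysis.

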5.3.5.1 Diagnosis versus Signs and Symptoms

For adverse events, a diagnosis (if known) should be recorded on the Adverse Event eCRF rather than individual signs and symptoms (e.g., record only liver failure or hepatitis rather than jaundice, asterixis, and elevated transaminases). However, if a constellation of signs and/or symptoms cannot be medically characterized as a single diagnosis or syndrome at the time of reporting, each individual event should be recorded on the Adverse Event eCRF. If a diagnosis is subsequently established, all previously reported adverse events based on signs and symptoms should be nullified and replaced by one adverse event report based on the single diagnosis, with a starting date that corresponds to the starting date of the first symptom of the eventual diagnosis.

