6.5 SAFETY ANALYSES

Safety will be assessed through summaries of adverse events, changes in laboratory test results, and changes in selected vital signs. Safety analyses will be performed for treated patients by cohort. Selected analyses will be performed by BCG dose level.

All adverse events with onset on or after treatment on Day 1 (treatment-emergent adverse events) will be summarized by mapped term, appropriate thesaurus levels, and NCI CTCAE v4 toxicity grade. All adverse events, NCI CTCAE v4 Grade ≥ 3 adverse events, adverse events leading to withdrawal of treatment and serious adverse events will be summarized overall and for treatment related events. In addition, all deaths including cause of death will be summarized. All adverse events and deaths will be listed.

All DLTs will be listed for DLT-evaluable patients (see Section 3.1.3 for a definition of DLT-evaluable patients).

NCI CTCAE v4 Grade 3 and 4 laboratory data will be listed; in addition changes in selected laboratory data will be summarized by grade with use of the NCI CTCAE v4. Selected vital signs and selected laboratory data will be summarized. The incidence of antibodies to atezolizumab will be summarized.

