Table 7 *Management Guidelines for Infusion-Related Reactions and Cytokine-Release Syndrome (cont.)*

Grade 2^a Fever^b with hypotension not requiring vasopressors and/or Hypoxia requiring low-flow oxygen^d by nasal cannula or blow-by
	
 • Immediately interrupt infusion. • Upon symptom resolution, wait for 30 minutes and then restart infusion at half the rate being given at the time of event onset. • If symptoms recur, discontinue infusion of this dose. • Administer symptomatic treatment.^c • For hypotension, administer IV fluid bolus as needed. • Monitor cardiopulmonary and other organ function closely (in the ICU, if appropriate). Administer IV fluids as clinically indicated, and manage constitutional symptoms and organ toxicities as per institutional practice. • Rule out other inflammatory conditions that can mimic CRS (e.g., sepsis). If no improvement within 24 hours, initiate workup and assess for signs and symptoms of HLH or MAS as described in this appendix. • Consider IV corticosteroids (e.g., methylprednisolone 2 mg/kg/day or dexamethasone 10 mg every 6 hours). • Consider anti-cytokine therapy.^e • Consider hospitalization until complete resolution of symptoms. If no improvement within 24 hours, manage as per Grade 3, that is, hospitalize patient (monitoring in the ICU is recommended), permanently discontinue atezolizumab, and contact Medical Monitor. • If symptoms resolve to Grade 1 or better for 3 consecutive days, the next dose of atezolizumab may be administered. • For subsequent infusions, consider administration of oral premedication with antihistamines, anti-pyretics, and/or analgesics and monitor closely for IRRs and/or CRS. • If symptoms do not resolve to Grade 1 or better for 3 consecutive days, contact Medical Monitor.
--	---

Appendix 12

Risks Associated with Atezolizumab and Guidelines for Management of Adverse Events Associated with Atezolizumab (cont.)

Table 7 *Management Guidelines for Infusion-Related Reactions and Cytokine-Release Syndrome (cont.)*

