Immune-mediated myositis, Grade 4	
 • Permanently discontinue atezolizumab and contact Medical Monitor. ^c • Refer patient to rheumatologist or neurologist. • Initiate treatment as per institutional guidelines. • Respiratory support may be required in more severe cases. • Initiate treatment with corticosteroids equivalent to 1–2 mg/kg/day IV methylprednisolone, or higher-dose bolus if patient is severely compromised (e.g., cardiac or respiratory symptoms, dysphagia, or weakness that severely limits mobility); convert to 1–2 mg/kg/day oral prednisone or equivalent upon improvement. • If event does not improve within 48 hours after initiating corticosteroids, consider adding an immunosuppressive agent. • If event resolves to Grade 1 or better, taper corticosteroids over ≥1 month.

^a Atezolizumab may be withheld for a longer period of time (i.e., >12 weeks after event onset) to allow for corticosteroids (if initiated) to be reduced to the equivalent of ≤10 mg/day oral prednisone. The acceptable length of the extended period of time must be agreed upon by the investigator and the Medical Monitor.

^b If corticosteroids have been initiated, they must be tapered over ≥1 month to the equivalent of ≤10 mg/day oral prednisone before atezolizumab can be resumed.

^c Resumption of atezolizumab may be considered in patients who are deriving benefit and have fully recovered from the immune-mediated event. Patients can be re-challenged with atezolizumab only after approval has been documented by both the investigator (or an appropriate delegate) and the Medical Monitor.

Appendix 12

Risks Associated with Atezolizumab and Guidelines for Management of Adverse Events Associated with Atezolizumab (cont.)

HEMOPHAGOCYTIC LYMPHOHISTIOCYTOSIS AND MACROPHAGE ACTIVATION SYNDROME

Immune-mediated reactions may involve any organ system and may lead to hemophagocytic lymphohistiocytosis (HLH) and macrophage activation syndrome (MAS), which are considered to be potential risks for atezolizumab.

Patients with suspected HLH should be diagnosed according to published criteria by McClain and Eckstein (2014). A patient should be classified as having HLH if five of the following eight criteria are met:

- *Fever $\geq 38.5^{\circ}\text{C}$*
- *Splenomegaly*
- *Peripheral blood cytopenia consisting of at least two of the following:*
 - *Hemoglobin < 90 g/L (9 g/dL) (< 100 g/L [10 g/dL] for infants < 4 weeks old)*

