 - *Platelet count $< 100 \times 10^9/\text{L}$ (100,000/ μL)*
 - *ANC $< 1.0 \times 10^9/\text{L}$ (1000/ μL)*
- *Fasting triglycerides > 2.992 mmol/L (265 mg/dL) and/or fibrinogen < 1.5 g/L (150 mg/dL)*
- *Hemophagocytosis in bone marrow, spleen, lymph node, or liver*
- *Low or absent natural killer cell activity*
- *Ferritin > 500 mg/L (500 ng/mL)*
- *Soluble interleukin 2 (IL-2) receptor (soluble CD25) elevated ≥ 2 standard deviations above age-adjusted laboratory-specific norms*

Patients with suspected MAS should be diagnosed according to published criteria for systemic juvenile idiopathic arthritis by Ravelli et al. (2016). A febrile patient should be classified as having MAS if the following criteria are met:

- *Ferritin > 684 mg/L (684 ng/mL)*
- *At least two of the following:*
 - *Platelet count $\leq 181 \times 10^9/\text{L}$ (181,000/ μL)*
 - *AST ≥ 48 U/L*
 - *Triglycerides > 1.761 mmol/L (156 mg/dL)*
 - *Fibrinogen ≤ 3.6 g/L (360 mg/dL)*

Patients with suspected HLH or MAS should be treated according to the guidelines in [Table 14](#).

Appendix 12

Risks Associated with Atezolizumab and Guidelines for Management of Adverse Events Associated with Atezolizumab (cont.)

Table 14 Management Guidelines for Suspected Hemophagocytic Lymphohistiocytosis or Macrophage Activation Syndrome

Event	Management
Suspected HLH or MAS	
 • Permanently discontinue atezolizumab and contact Medical Monitor. • Consider patient referral to hematologist. • Initiate supportive care, including intensive care monitoring if indicated per institutional guidelines. • Consider initiation of IV corticosteroids and/or an immunosuppressive agent. • If event does not improve within 48 hours after initiating corticosteroids, consider adding an immunosuppressive agent. • If event resolves to Grade 1 or better, taper corticosteroids over ≥ 1 month.

HLH =hemophagocytic lymphohistiocytosis; MAS =macrophage activation syndrome.

REFERENCES

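### Appendix 12 prints each ferritin cut-off for HLH and MAS in two units that differ 1000-fold, so one patient can be classified both ways for MAS

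*Combined protocol and SAP*

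**What the plan says.** The section of Appendix 12 on HLH and MAS lists diagnostic criteria for each condition, most of them in two units.

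- **HLH.** The rule is "A patient should be classified as having HLH if five of the following eight criteria are met". One of the eight is "Ferritin > 500 mg/L (500 ng/mL".
- **MAS.** The rule is "A febrile patient should be classified as having MAS if the following criteria are met". The list requires "Ferritin > 684 mg/L (684 ng/mL", together with at least two of four findings on platelets, AST, triglycerides and fibrinogen.

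Three other places bear on how these lines are used:

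- Table 7 of Appendix 12 (infusion-related reactions and cytokine-release syndrome) tells sites, for Grade 2 to 4 events that have not improved within 24 hours, to "initiate workup and assess for signs and symptoms of HLH or MAS as described in this appendix".
- Section 5.3.5.1 says that "a diagnosis (if known) should be recorded on the Adverse Event eCRF rather than individual signs and symptoms". Section 6.5 says that treatment-emergent adverse events "will be summarized by mapped term, appropriate thesaurus levels, and NCI CTCAE v4 toxicity grade".
- Management is tied to suspicion: "Patients with suspected HLH or MAS should be treated according to the guidelines in" Table 14 of the appendix.

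No other ferritin threshold appears in the document, and nothing corrects these two.

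**The concern.** A value in mg/L and the same value in ng/mL cannot be the same concentration, so each line states two different thresholds. These lines are in current, directive text and set the terms on which a patient is to be classified. Ferritin is a required element of the MAS rule, so the choice of figure alone can decide the MAS classification.

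A site that applied the mg/L figure could fail to classify a MAS case and record another diagnosis. That diagnosis would go onto the eCRF in place of the signs and symptoms, and would be the term summarized. Section 5.1.1 names HLH and MAS as potential risks of atezolizumab, so this could change the count for a risk that the protocol singles out.

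**Working it through.** **Inputs**, all from the HLH and MAS lists in Appendix 12: the HLH ferritin pair (500 mg/L, 500 ng/mL), the MAS ferritin pair (684 mg/L, 684 ng/mL), the two classification rules, and the other dual-unit pairs for comparison.

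**Step 1: unit conversion.** 1 mg/L = 1,000,000 ng per 1,000 mL = 1,000 ng/mL.

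- HLH: 500 mg/L × 1,000 = 500,000 ng/mL, against 500 ng/mL printed. Ratio 1,000.
- MAS: 684 mg/L × 1,000 = 684,000 ng/mL, against 684 ng/mL printed. Ratio 1,000.
- In the other direction, 500 ng/mL = 0.5 mg/L = 500 µg/L, and 684 ng/mL = 0.684 mg/L = 684 µg/L.

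Neither printed equivalence can be reproduced. With µg/L in place of mg/L, both can.

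**Step 2: is this a general problem in the lists?** They hold 11 dual-unit pairs, 7 for HLH and 4 for MAS.

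| Item | List | Printed pair | Agrees? |
|---|---|---|---|
| Hemoglobin | HLH | 90 g/L, 9 g/dL | yes (90/10 = 9) |
| Hemoglobin, infants | HLH | 100 g/L, 10 g/dL | yes (100/10 = 10) |
| Platelets | HLH | 100 × 10^9/L, 100,000/µL | yes |
| ANC | HLH | 1.0 × 10^9/L, 1000/µL | yes |
| Triglycerides | HLH | 2.992 mmol/L, 265 mg/dL | yes (265/2.992 = 88.57) |
| Fibrinogen | HLH | 1.5 g/L, 150 mg/dL | yes (1.5 × 1000/10 = 150) |
| Ferritin | HLH | 500 mg/L, 500 ng/mL | **no, 1000-fold** |
| Platelets | MAS | 181 × 10^9/L, 181,000/µL | yes |
| Triglycerides | MAS | 1.761 mmol/L, 156 mg/dL | yes (156/1.761 = 88.59) |
| Fibrinogen | MAS | 3.6 g/L, 360 mg/dL | yes (3.6 × 1000/10 = 360) |
| Ferritin | MAS | 684 mg/L, 684 ng/mL | **no, 1000-fold** |

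The triglyceride pairs are judged by whether they imply the same conversion factor, which they do, so no outside constant is needed. Nine of 11 pairs agree. The two that fail are the ferritin pairs, and they fail in the same way.

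**Step 3: effect on the MAS rule.** Take a hypothetical febrile patient with platelets 150 × 10^9/L (at or below 181) and AST 60 U/L (at or above 48), so that two supporting findings are met.

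| Ferritin (ng/mL) | MAS by 684 ng/mL | MAS by 684 mg/L |
|---|---|---|
| 600 | no | no |
| 700 | yes | no |
| 2,000 | yes | no |
| 10,000 | yes | no |
| 100,000 | yes | no |
| 683,999 | yes | no |
| 684,001 | yes | yes |

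The two figures disagree for any ferritin above 684 and up to 684,000 ng/mL.

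**Step 4: effect on the HLH rule.** Take ferritin 2,000 ng/mL and vary how many of the other seven criteria are met.

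| Other criteria met | HLH by 500 ng/mL | HLH by 500 mg/L |
|---|---|---|
| 3 | no (4 of 8) | no (3 of 8) |
| 4 | yes (5 of 8) | no (4 of 8) |
| 5 | yes (6 of 8) | yes (5 of 8) |

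Ferritin decides HLH only when exactly four of the other seven are met. With five or more, HLH is met without it. With three or fewer, HLH is not met either way.

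**The case against.** The arithmetic is not in dispute. The case on the other side is that this is an editorial slip with little practical reach.

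- **Care does not depend on the cut-off.** Table 14 calls for permanent discontinuation of atezolizumab and contact with the Medical Monitor on suspicion alone. Events suggestive of cytokine-release syndrome or systemic inflammatory reaction syndrome are reportable under Section 5.2.3 whatever the ferritin. This stands and limits the consequence.
- **A plausible figure is on the same line.** The study runs at US sites, and the eligibility criteria in Section 4.1.1 give hemoglobin in g/dL and platelets per µL, the units that the Appendix 12 lists put in parentheses. Such a site may well read the ng/mL value. This makes misclassification less likely. It does not settle which figure governs, since the mg/L value is printed first.
- **The published criteria are cited as the authority.** A site that noticed the mismatch could look them up. One that did not notice would have no reason to.
- **The recording route is loose.** Section 5.3.5.1 applies to a diagnosis if known and does not tie the eCRF term to ferritin. All adverse events are also listed individually under Section 6.5. So a changed term is possible, not certain. The documents give no HLH or MAS frequency from which to say how many patients could be affected.
- **The text was read from a PDF, so µ might have been misread as m.** This cannot be fully excluded. It is unlikely, because the micro sign survives in the cell counts of the same lists and in µg/mL in Section 3.4.2, and both ferritin lines show the same error.

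These points bound the effect. They do not remove a 1000-fold contradiction from a mandatory diagnostic criterion.

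**Conclusion.** The concern holds. Both ferritin lines are wrong as written, each by a factor of exactly 1000. The two MAS figures give opposite classifications for a febrile patient with at least two supporting findings and ferritin above 684 and up to 684,000 ng/mL. For HLH the conflict arises only with exactly four of the other seven criteria met and ferritin above 500 and up to 500,000 ng/mL.

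The consequence is confined to which diagnosis is recorded and then tabulated. Treatment and atezolizumab discontinuation are unaffected, and so are the rules for adverse events of special interest and dose-limiting toxicity, the sample size and the efficacy analyses. It is still a wrong decision threshold in directive text and should be corrected.

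The conclusion assumes that the sponsor's page carries the units as read here. The contradiction itself does not depend on which unit was meant. That the ng/mL values are the intended ones is an inference: replacing one unit prefix makes both lines consistent. The cited criteria were not available to confirm it.

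**What to change.** Check both ferritin lines in Appendix 12 against the cited HLH and MAS criteria and against the original page. If the ng/mL values are intended, change mg/L to µg/L in both, so that they read 500 µg/L (500 ng/mL) and 684 µg/L (684 ng/mL). The cost is one unit prefix in each of two lines. It can go into the next amendment, and a separate safety letter is not needed.
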